Appendix B

Acronyms and Definitions

AF	Atrial Fibrillation
bpm	Beats per minute
CEC	Clinical Events Committee
cm	Centimetre
CRF	Case Report Form
DFT	Defibrillation Threshold Test
EC	Ethics Committee
ECG	Electrocardiogram
EIT	Electrode Insertion Tool
GCP	Good Clinical Practice
GUI	Graphical User Interface
HCP	Health Care Professional
Hz	Hertz
ICD	Implantable Cardioverter Defibrillator
J	Joules
KM	Kaplan Meier
LVEF	Left Ventricular Ejection Fraction
mA	Milliamperes
mm	Millimetre
ms	Millisecond
mV	MilliVolt
NSR	Normal Sinus Rhythm
NYHA	New York Heart Association
QOL	Quality of Life
PCMCIA	Personal Computer Memory Card International Association
ppm	Pulses per minute
RF	Radio Frequency
SCD	Sudden Cardiac Death
sec	Seconds
S-ICD	Subcutaneous ICD
SVT	Supra Ventricular Tachycardia
SVGA	Super Video Graphics Array
TV-ICD	Transvenous Implantable Cardioverter Defibrillator
VF	Ventricular Fibrillation
VT	Ventricular Tachyarrhythmia

Appendix D

Investigator Signature Page

Protocol Title:

Evaluation of E FactOrs ImpacTing Clinical Outcome and Cost EffectiveneSS of the S-ICD – The EFFORTLESS S-ICD Registry

Protocol Version:

AB, dated May 04, 2017

I, the undersigned, have read and understand the protocol specified above and agree on its content. I agree to perform and conduct the trial as described in the protocol and in accordance with applicable laws and regulations. In addition, when applicable, I agree to enlist subinvestigators who also agree to perform and conduct the trial as described in the protocol.

PRINCIPAL INVESTIGATOR:

Name: _____

Signature: _____

Date: _____

In the past the 10-year follow-up has been a key milestone for transvenous ICD systems, as the industry average transvenous ICD longevity is approximately 8 years³⁴ and transvenous lead failures occur around 8-10 years post implant.⁹

The first generation S-ICD (SQ-RX) has a projected longevity of approximately 5 years. However the EFFORTLESS S-ICD Registry documents operational and clinical outcomes only up to 5 years after the implant. For this reason little data is available on the success of S-ICD System replacements. This includes pulse generator replacements because of elective replacement indicator (ERI) battery status and electrode replacements. In addition some patients require over time a system replacement due to an indication change, as for example a need for pacing.

This Sub-Study will extend the Registry in order to collect long-term follow-up data on a subset of EFFORTLESS S-ICD patients to achieve an average of approximately 8 years of follow-up from index procedure. Approximately 200 patients will be enrolled in the Sub-Study at a sub-set of EFFORTLESS S-ICD sites. The Sub-Study patients will preferably be recruited from the active EFFORTLESS S-ICD patient population. Patients, who have already completed the EFFORTLESS S-ICD Registry in the past, shall be considered secondarily for participation in the Sub-Study. To reduce the selection bias, the patients shall be screened and approached for consent consecutively.

The expected duration of the extension phase is approximately 72 months.

The following data will be analysed in addition of the main study endpoints:

Primary Analysis

- Rate of long-term S-ICD system-related adverse events
- S-ICD replacements for functionality (e.g. pacing, CRT, ATP etc.)
- Device longevity

Secondary Analysis

- Rate of electrode failures and revisions, including the reason for revision
- Rate of device failures and revisions, including the reason for revision
- Rate of complications related to the S-ICD replacements
- Appropriate therapy for VT/VF
- Inappropriate shock therapy (e.g. atrial fibrillation, supraventricular tachycardia)

The following observational data will be collected and analysed additionally to the main study:

- Generator changes/electrode revisions
- VF induction testing at replacement
- Complications associated with S-ICD to TV-ICD change
- Additional invasive interventions (e.g. VT ablation)
- Use of anti-arrhythmic drugs
- Ventricular cycle length of episodes
- Duration (non-sustained episodes)

Patients enrolled in the Sub-Study must meet all inclusion criteria and none of the exclusion criteria as described below.

Inclusion Criteria

1. Subjects who are actively enrolled in the EFFORTLESS S-ICD Registry OR Subjects who completed the 5-year follow-up in the EFFORTLESS S-ICD Registry. All clinical events, spontaneous and induced episode data and system replacement or revision data since the last EFFORTLESS S-ICD Annual Follow-Up of the main study must be available in medical files or equivalent.
2. Subjects who are actively implanted with an S-ICD pulse generator (SQ-RX, EMBLEM or EMBLEM MRI) and an S-ICD electrode (Q-TRAK or EMBLEM) or any other future commercial available versions
3. Willing and able to provide written informed consent or have informed consent as provided by a legal representative and willing to participate in all testing and follow-ups as described the Sub-Study protocol
4. Age 18 or above, and of legal age to give informed consent specific to national laws

Exclusion Criteria

1. Subjects with device replacement from the S-ICD to a transvenous ICD
2. Subjects with unipolar pacemakers or implanted devices that revert to unipolar pacing
3. Subjects that are participating in any other investigational study that may interfere with interpretation of the Registry results, without the written approval of Boston Scientific

Once a patient is enrolled in the Sub-Study, the visit schedule according to Table 8 must be followed. Patients, who have still been actively enrolled in the main EFFORTLESS S-ICD Registry will be waived from the visit requirements as described in Table 3 (Section 7.1) and will be followed-up according to Table 8 only.

Table 8: Summary of information requested for the Sub-Study

	Sub-Study Enrolment Visit	Sub-Study Annual Follow-up Visit	S-ICD System Replacement or Revision
Sub-Study Informed Consent	X	--	--
Demographics	X	--	--
Antiarrhythmic Medication	X	X	X
Episodes (Spontaneous or Induced)	X	X	X ^A
Final Summary Report	X	X	X ^A
Surgical documentation	--	--	X
VT/VF Defibrillation Testing	X ^A	--	X ^A
Adverse Events	X	X	X

^A If done/If available

Sub-Study Enrolment Visit

The patients shall be enrolled in the Sub-Study at the earliest convenience. A patient is considered enrolled for the Sub-Study after providing written informed consent in accordance with applicable local and national guidelines and/or Ethics Committee (EC) requirements. Sites will be notified when enrolment in the Sub-Study is complete.

The informed consent date, patient demographics and the antiarrhythmic drugs will be collected for all enrolled patients. All device related events, including spontaneous or induced episodes and system replacements or revisions, if applicable, and all adverse events, which occurred since the last EFFORTLESS S-ICD Annual Follow-up will be documented retrospectively.

Table 9 lists the data that will be requested at the Enrolment visit. For the data collection requirements of replacements and revisions please refer to Table 11.

Table 9: Sub-Study Enrolment Visit Source Documentation Requirements

Data Collection	Retention of Originals
Sub-Study Patient Consent Form Demographics (Physical) Antiarrhythmic Medications All Adverse Events since last reported EFFORTLESS S-ICD Annual FU	Retain at center
Spontaneous Episodes ± therapy, including Episode reports since last EFFORTLESS S-ICD Annual FU S-ICD Final Summary Report	Retain the original at the center and submit a copy to Boston Scientific

Sub-Study Annual Follow-Up Visits

The first Annual Follow-up will be done 12 month +/- 90 days after the Sub-Study Enrolment Visit. Afterwards data will continue to be collected once annually. It is recommended that the subsequent Annual Follow-ups occur 24, 36, 48 and 60 months +/- 90 days from the date of the Sub-Study Enrolment Visit.

The subjects participation in the Sub-Study is considered concluded upon completion of the 5th Annual Sub-Study Follow-up, the patient withdraws from the Sub-Study (or is withdrawn including for reasons of death) or is Lost to Follow-Up.

All antiarrhythmic medication changes, the current status of the S-ICD System, all episodes and adverse event that occurred during the period prior to the annual data follow up, will be collected.

All programming is at the discretion of the Investigator. Table 10 lists all the data that will be required from Annual Follow-ups, if available.

Table 10: Sub-Study Annual Follow-Up Source Documentation Requirements

Data Collection	Retention of Originals
Antiarrhythmic medication changes Adverse Events	Retain at center
Episodes ± therapy, including Episode report S-ICD Final Summary Report	Retain the original at the center and submit a copy to Boston Scientific

S-ICD System Replacements and Revisions

In the event that any component of the S-ICD System is surgically revised or replaced (including the replacement with a transvenous ICD) after the initial implant procedure, an additional “S-ICD System Procedure” form must be used to record changes to the system and to document the surgical procedure.

Table 11 lists the data that will be requested in case of a system replacement or revision.

Table 11: System replacement or revision Source Documentation Requirements

Data Collection	Retention of Originals
Reason for replacement or revision Surgical Documentation including: 
 • Medications (antibiotics; type of anesthesia etc.) • Medical notes documenting implant time; use of fluoroscopy etc. • Chest X-rays (posterioranterior & lateral), if applicable • Implanted Product and accessories utilized for S-ICD System (model/serial/lot/batch/etc.) Adverse Events	Retain at center
S-ICD Final Summary Reports of the old and new S-ICD pulse generator, if applicable VT/VF Defibrillation Testing (programmer printout, electrode & shock impedance), if applicable	Retain the original at the center and submit a copy to Boston Scientific

Sub-Study patients, who have an S-ICD pulse generator replacement or device explant (e.g. due to infection, skin erosion or an indication change) shall continue to be followed within the Sub-Study.

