Extension Phase Sub-Study (Appendix E)	
The Sub-Study will extend the EFFORTLESS S-ICD Registry in order to achieve an average of approximately 8 years of follow-up from index procedure. The expected duration of the extension phase is approximately 72 month.
 
A subgroup of approximately 200 patients will be enrolled in the Sub-Study at a subset of EFFORTLESS S-ICD sites. These patients will be followed once annually for additional 5 years in the EFFORTLESS S-ICD Registry from the time of consent into the Extension Phase.
 
The following data will be analysed in addition of the main study endpoints:
 
Primary Analysis
 
 Rate of long-term S-ICD system-related adverse events S-ICD replacements for functionality (e.g. pacing, CRT, ATP etc.) Device longevity 
Secondary Analysis
 
 Rate of electrode failures and revisions, including the reason for revision Rate of device failures and revisions, including the reason for revision Rate of complications related to the S-ICD replacements Appropriate therapy for VT/VF Inappropriate shock therapy (e.g. atrial fibrillation, supraventricular tachycardia) 
The In- and Exclusion Criteria for the Sub-Study are the following:
 
Inclusion Criteria
 
 Subjects who are actively enrolled in the EFFORTLESS S-ICD Registry OR Subjects who completed the 5-year follow-up in the EFFORTLESS S-ICD study. 	

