3.0 Purpose and Objectives

The purpose of the Evaluation of Factors Affecting Clinical Outcome and Cost Effectiveness of the S-ICD or "EFFORTLESS S-ICD" Registry, is to document early, mid-and long-term operational and clinical outcomes associated with the implantation of the Boston Scientific S-ICD system. The evaluation will include documenting the patients' perception of his/her therapy through Quality of Life (QOL) assessments. The study will be conducted at approximately 50 clinical centres worldwide in patients requiring an ICD for the treatment of ventricular tachyarrhythmias.

Data will be collected to evaluate perioperative (30 day post implant), mid- (360 day post implant) and long-term (up to 60 months) clinical complication rates associated with the implantation of the S-ICD system as well as the percentage of patients experiencing inappropriate shocks for AF and/or SVT. The Registry will also include analysis of resource utilization and costs based on measures of clinical outcome such as complication rates, unscheduled hospitalizations and length of stay. The objective will be to enable comparison of costs of the S-ICD system versus a standard transvenous system.

The Sub-Study (see Appendix E) will extend the EFFORTLESS S-ICD Registry in order to collect long-term follow-up data on a subset of EFFORTLESS patients to achieve an average of approximately 8 years of follow-up from index procedure.

The purpose of the Sub-Study is to document the reason for S-ICD system replacements or revisions and describe the associated clinical events and outcomes.

Data will be collected in conformance with the "Declaration of Helsinki", ISO 14155:2009 and the laws and regulations of the country in which the research is conducted.

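### Does leaving out the analysis set and time zero for functionality replacements bias the Extension Sub-Study result?

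*Combined protocol and SAP*

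**What the plan says.** Appendix E lists "S-ICD replacements for functionality (e.g. pacing, CRT, ATP etc.)" as one of three primary Sub-Study analyses. Several neighbouring items are worded as rates; this one is not. No analysis set, denominator, time origin or estimator is attached to it.

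Eligibility depends on device status at consent. Entrants are "Subjects who are actively implanted with an S-ICD pulse generator (SQ-RX, EMBLEM or EMBLEM MRI)" together with an S-ICD electrode, and "Subjects with device replacement from the S-ICD to a transvenous ICD" are excluded. Recruitment favours active Registry patients: "Patients, who have already completed the EFFORTLESS S-ICD Registry in the past, shall be considered secondarily for participation in the Sub-Study".

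Two time anchors appear. The extension is meant "to achieve an average of approximately 8 years of follow-up from index procedure". Follow-up itself runs for "additional 5 years in the EFFORTLESS S-ICD Registry from the time of consent into the Extension Phase" (Synopsis), with later annual visits recommended at "24, 36, 48 and 60 months +/- 90 days from the date of the Sub-Study Enrolment Visit" (Appendix E).

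Section 5.0 names the Sub-Study as within its scope, takes every enrolled Registry patient into the analysis and calls the analyses descriptive. Section 5.5 allows linear rates or Kaplan-Meier for long-term event rates. Section 5.7 censors drop-outs and requires the number of data behind each reported variable to be given. Section 3.0 gives the Sub-Study's purpose as being to "document the reason for S-ICD system replacements or revisions" and to describe the related events and outcomes.

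**The concern.** The eligibility rules and the 8-year description together suggest immortal time. A patient who gave up the S-ICD for a transvenous system in year 2, because pacing had become necessary, cannot enter. Everyone who does enter has therefore passed the years before consent without that event. If those years went into the denominator, they would add person-time in which the event could not be observed, and the rate would fall in the direction that flatters the device. Approaching patients consecutively for consent does not help, because the early switchers are removed by eligibility and not by who is asked.

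The stake is a primary Sub-Study result. The same 200 patients could yield about 7% presented as an 8-year figure, where the whole Registry would give about 11%. Section 5 does not mention delayed entry.

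**Working it through.** **Inputs.** From the documents: mean follow-up from index of about 8 years, 5 years of follow-up after consent, about 200 entrants and a Registry of about 1000. Inferred: mean entry time e = 8 − 5 = 3 years; I also try 1 and 5 years. Assumed, because the documents give no switch or death rate: a constant switch hazard h of 0.5%, 1.5% or 3% per year, with no deaths unless stated.

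**Entrants counted from index.** Mean post-consent time at risk is PT = (1 − exp(−5h))/h. All events fall in PT, but the denominator is e + PT, so the ratio to the true rate is PT/(e + PT).

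| h per year | PT (years) | e = 1 | e = 3 | e = 5 |
|---|---|---|---|---|
| 0.5% | 4.938 | 0.832 | 0.622 | 0.497 |
| 1.5% | 4.817 | 0.828 | 0.616 | 0.491 |
| 3% | 4.643 | 0.823 | 0.607 | 0.481 |

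The shortfall is about 38-39% at 3 years, and 17% to 52% over the whole table. With deaths at 2-5% per year and e = 3, replacing h by h + deaths in PT gives ratios of 0.58-0.61.

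On the cumulative scale at h = 1.5% and e = 3:
- from index in entrants: 1 − exp(−5 × 0.015) = 7.2%;
- true 8-year value: 1 − exp(−8 × 0.015) = 11.3%;
- relative shortfall: 1 − 7.2/11.3 = 36%.

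If the hazard is not constant but still reaches 11.3% at 8 years (Weibull), the entrant figure is 5.8% for a falling hazard (shape 0.7, 49% low) and 8.8% for a rising one (shape 1.5, 22% low).

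**All Registry patients counted from index (Section 5.0).** Early switches are now counted. The only stretch that is event-free by selection is the gap between finishing the Registry and consenting, and only among completers who join. With completer share f and gap g years, the 8-year value is approximately 1 − exp(−h(8 − f·g)). At h = 1.5%:

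| f | g = 0.5 | g = 1 | g = 1.5 |
|---|---|---|---|
| 10% | 11.24% | 11.17% | 11.11% |
| 25% | 11.14% | 10.97% | 10.81% |

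Against 11.31%, the shortfall is 0.07 to 0.50 percentage points. For scale, Section 5.6, Table 2 gives ±2.0% at a 90% event-free rate with 900 patients, and 1.96 × √(0.9 × 0.1/900) = 1.96 points reproduces it. The same formula with 11.3% and 1000 patients gives 1.96 × √(0.113 × 0.887/1000) = 1.96 points. That is a best case, since only about 200 patients are followed through the later years. The bias is at most about a quarter of that half-width (0.50/1.96 = 0.26).

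Formal delayed entry for completers removes this remainder. With f = 25% and g = 1 it moves the estimate from 10.97% to 11.31%, about 0.3 points.

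**Entrants counted from consent.** Events and person-time both start at consent, so the ratio is 1.00 under a constant hazard. The result is conditional on still having an S-ICD at entry. About 200 × 7.2% ≈ 14 events are expected over 5 years. For 14/200 = 7.0% the exact 95% interval is 3.9-11.5%.

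**Tabulation by reason.** Counting replacements and listing their reasons, which is what the stated purpose calls for, uses no person-time and so has no immortal-time error.

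**The case for a change.** The strongest case for amending the plan is that a descriptive rate still needs a denominator and an origin, and this is a primary analysis. Section 5.0 gives a population but no time zero. Data beyond 5 years exist only for entrants, and Appendix E speaks of a subset followed for 8 years from index. An analyst could therefore put the 200 entrants into a Kaplan-Meier curve from index, and the error would favour the device.

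What stands is that the text is incomplete, that the arithmetic for that one analysis is right, and that such a figure presented as an 8-year rate would mislead.

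Three things limit its force. First, the 8 years describe how long patients will have been followed; nothing makes index the origin of a rate in entrants alone, and the only population sentence points to the whole Registry. Second, Section 5.7 requires the number behind each variable, so a result on about 200 patients cannot pass for one on about 1000. That leaves only index versus consent to be stated among entrants, which an ordinary report does. Third, the 38% assumes no qualifying event before entry. The item's examples are open-ended, and a generator change from one S-ICD to another for added function would not bar entry; if such changes count, the shortfall is smaller.

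One practical limit remains whatever the wording. The main-Registry revision form is optional (Section 7.7), and the reason for replacement is a listed item only in Table 11 of Appendix E. Reasons in years 0-5 may therefore be incomplete, although system status and clinical events are requested annually (Table 7). A sentence on analysis set and origin would not cure that.

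**Conclusion.** No change is needed. The plan leaves out a detail; it does not prescribe a biased analysis. The large shortfall (about 38% at an inferred 3-year mean entry, 17-52% for 1 to 5 years) belongs only to entrants counted from index, which the documents do not set out. Under Section 5.0 as written, the bias is 0.07 to 0.50 points on 11.3%, well inside sampling error. From consent it is nil, and for a count by reason it does not arise. Delayed entry for completers would gain about 0.3 points.

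These sizes rest on an assumed hazard (1.5% per year for the cumulative figures), on roughly constant risk, on a mean entry inferred as 8 − 5, and on assumed completer shares of 10-25% with gaps of 0.5-1.5 years. The endpoint is descriptive, with no hypothesis or success threshold. An analyst reporting a rate would name the patients and the origin as a matter of course, and would describe a rate in entrants as conditional on having an S-ICD at entry. Device longevity and S-ICD-to-S-ICD changes are hardly affected, because those patients remain eligible.
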